### 5.2.7. Laboratory Examination

According to the SWEDEGRAFT protocol, all patients receive a blood sample to measure renal function to ensure an eGRF/1.73m^2 (CKD-EPI)  $\geq 35$  ml/min prior to CTA. We supplement measurements of haemoglobin, and brain natriuretic peptide (BNP), in order to fully adjust our results for laboratory findings, which are important risk factors for heart failure.

### 5.2.8. In-hospital details derived from electronic patient record

- Details from the operations report (preoperative lesions, grafts incl. flow and pulsatile index, length of surgery, length of cardiopulmonary bypass, cross-clamp time, areas of incomplete revascularization)
- Signs of perioperative myocardial damage (postoperative CK-MB, ECG, and echocardiography)

### 5.2.9. Long-term Major Adverse Cardiac and Cerebrovascular Events

According to SWEDEGRAFT protocol, the MACCE rate is registered at 2-year follow-up after review of the electronic patient record. MACCE are defined as:

- Death from any cause (cardiovascular and non-cardio-vascular mortality).
- Myocardial infarction
- Repeat hospitalization due to cardiac cause
- Cerebrovascular accident
- Repeat revascularization

We intend to review the electronic patient record for MACCE 5- and 10 years after surgery in order to correlate cardiac function to long-term clinical outcome.

### 5.3. Schedule of evaluations

	Initial Hospitalization	24-30 months Follow-up	5-year Follow-up	10-year Follow-up
Initiation procedures				
Eligibility*	●			
Demographics*	●			
Informed consent & randomization*	●			
Surgery*	●			
Investigations				
Echocardiography	●*(2D)	●(2D/3D)		
Haemoglobin, ProBNP		●		
12-lead ECG*		●		
eGFR*		●		
CTA*		●		
SAQ-7*		●		
NYHA class		●		
Borg CR 10®		●		
MACCE		●*	●	●

Borg CR 10®= BORG category-ratio 10 scale; CT= Computed Tomography; eGFR= estimated Glomerular Filtration Rate; ECG= Electrocardiogram; MACCE = Major Adverse Cardiac and Cerebrovascular Events; NYHA= New York Heart Association; Seattle Angina Questionnaire= SAQ-7. \* Elements of the main SWEDEGRAFT study to be included in the Right-Heart-Substudy

## 6. SAFETY ASPECTS

### 6.1. Insurance

The investigators will be covered by the liability and work injury insurance taken out by Aarhus University Hospital. Participants are covered by the act on complaints and compensation within the health care system.

### 6.2. Adverse events

All patients included in the study are given standard care. Per SWEDEGRAFT protocol, information about wound healing in the harvesting site on the leg are registered. No adverse events are anticipated in this observational study in conjunction with:

- Transthoracic echocardiography
- Acquisition of the NYHA class and Borg CR 10®
- Determination of haemoglobin and ProBNP in the blood sample drawn for eGFR analysis
- Review of the electronic patient record at 5- and 10-years.

## 7. STATISTICS CONSIDERATIONS

### 7.1. General design issues

The SWEDEGRAFT study is an open-label randomized trial. However, evaluation of health status by means of questionnaires and echocardiographies will be performed by a study nurse and investigators blinded regarding the allocation to ensure unbiased ascertainment of outcomes.

### 7.2. Determination of Sample Size and randomization

The present Right-Heart-Substudy aims to determine the prevalence and scale of RV dysfunction as measured by 3D RV EF two years after CABG. To the best of our knowledge, no prior study has described the prevalence of chronic RV dysfunction after CABG applying this technology. The best prospective study available in this field of enquiry offers a follow-up of up to one year after CABG using 2D echocardiographic measurements (Roshanali 2008).

As a prevalence study there is no hypothesis to test and the size of the study is determined by how accurately we want to determine the prevalence. Based on the formula suggested by Viechtbauer et al., a sample size of N=194 will suffice to identify impaired 3D RV EF (< 45%) with a prevalence down to 2% with a 98% confidence (Viechtbauer 2015). In order to ensure a complete dataset, we aim to include a total of 230 participants.

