## 1. AIM AND STUDY OBJECTIVES

### 1.1. Hypothesis

We propose that right ventricular (RV) systolic function is essentially preserved two years after coronary artery bypass grafting (CABG). Being a prevalence study, there is no actual hypothesis to test.

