### 5.3.2. Preoperative 2D-Echocardiography

A routine 2D-echocardiography has been performed in all patients two to three months prior to CABG at Aarhus University Hospital to assess cardiac function including contractility, chamber size, hypertrophy, valvular dysfunction, and pericardial or pleural effusions. The echocardiographic images were digitally stored for offline analysis using commercially available software (EchoPAC version 203, GE-Vingmed Ultrasound, Horten, Norway).

The echocardiographic RV parameters available on preoperative as compared to follow-up 2D/3D echocardiography including normal cutoff values are depicted in the following chart.

RV Parameters	Preop ECHO	Follow-up ECHO	Normal cutoff value	References
RV 3D EF Right ventricular ejection fraction (3D)		●	> 45 %	Lang 2015
RV-FWS Right ventricular free wall strain		●	$-28.7\% \pm 4.1$	Meris 2010
RV-GLS Right Ventricular Global Longitudinal Strain	(●)	●	-	-
RV FAC Right ventricular fractional area change	(●)	●	> 35%	Lang 2015
TAPSE Tricuspid Annular Plane Systolic Excursion	(●)	●	> 17 mm	Lang 2015
Tricuspid S' velocity Peak systolic tricuspid annular velocity		●	> 9.5 m/s	Lang 2015
RAV Right Atrial Volume	●	●	< 30 mL/m 	Lang 2015
RAESA Right Atrial End-Systolic Area	●	●	< 18 mm 	Lang 2015
RVD Right Ventricular Diameter	●	●	Base < 41 mm Midventricular < 35 mm Length < 83 mm	Lang 2015

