## 14 PERSPECTIVES

In Denmark, more than 45 CABG operations are conducted per 100 000 inhabitants per year (Eurostat 2020). The current study will clearly define the prevalence and scope of significant RV depression following this common surgical procedure. We expect to resolve the apparent contradiction of undisputable echocardiographic signs of RV depression after cardiac surgery and the lack of clinical signs of RV failure.

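### A 3D RV EF below the 45% normal cutoff, measured once after surgery with no preoperative value or control group, cannot by itself show RV depression due to CABG

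*Protocol*

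**What the plan says.** Section 7.2 of the protocol sizes the study by a formula for problem detection. It says that 194 patients "will suffice to identify impaired 3D RV EF (< 45%) with a prevalence down to 2% with a 98% confidence", and it raises the recruitment target to 230 to allow for incomplete data. It adds: "As a prevalence study there is no hypothesis to test".

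The chart in 5.3.2 gives the same 45% for RV 3D EF in the column "Normal cutoff value". It cites a source but gives no percentile, mean or SD for that limit. The chart marks RV 3D EF at follow-up only, because the preoperative echocardiography was 2D. All participants come from a trial in which every patient had CABG (3.1, 5.2).

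The protocol's reading of the result goes beyond a proportion at one time point:

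- The synopsis gives the primary objective as the long-term impact of CABG on RV function.
- Section 1.2 asks about an association between CABG and RV depression.
- Section 14 says: "The current study will clearly define the prevalence and scope of significant RV depression following this common surgical procedure".
- Section 1.1 proposes instead that "right ventricular (RV) systolic function is essentially preserved two years after coronary artery bypass grafting (CABG").

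The only before-and-after comparison is the 2D decrement in RV function listed in 3.3.

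**The concern.** A limit of normal normally leaves some healthy subjects on the wrong side of it. Counting patients below it gives a valid prevalence of values below the limit. It does not separate three groups: people who were always in the lower tail, people whose RV was already impaired before surgery, and people whose RV function fell after CABG. A preoperative 3D value, a comparison group or a stated background share would help to separate them. For 3D RV EF the protocol has none of these.

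What is at stake is the conclusion. A low prevalence could be presented as preserved function, in line with 1.1, or as RV depression after surgery, in line with section 14. The protocol names no reference figure that would decide between the two.

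**Working it through.** **Inputs from the protocol.** Case: 3D RV EF below 45% (7.2). Lowest prevalence to be detected: 2% (7.2). Confidence: 98% (7.2). N = 194, with 230 to be recruited (7.2).

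**Input not in the protocol.** The share p0 of unaffected people below 45%. It is assumed here and varied widely.

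**Step 1: reproduce the plan's figure.** n = ln(1 − 0.98) / ln(1 − 0.02) = −3.9120 / −0.020203 = 193.6, rounded up to 194. Check: 1 − 0.98^194 = 0.980. The sample size is right for what it claims, which is a 98% chance of seeing at least one case if the prevalence is 2%.

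**Step 2: apply the same calculation to 194 unaffected patients.** Expected cases = 194 × p0. Chance of at least one = 1 − (1 − p0)^194.

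| Assumed p0 | Expected cases of 194 | Chance of at least one |
|---|---|---|
| 0.13% (about mean − 3 SD) | 0.25 | 22% |
| 0.5% | 0.97 | 62% |
| 1% | 1.9 | 86% |
| 2.5% | 4.9 | 99.3% |
| 5% | 9.7 | >99.9% |

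With a limit at the 2.5th percentile, unaffected patients would produce at least one case about as surely as the 2% prevalence in the plan (98.0%). With a very strict limit they usually would not.

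**Step 3: how many cases would exceed the background?** The smallest count whose lower exact (Clopper-Pearson) 95% limit lies above p0 is:

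- p0 = 1%: 6 of 194 (3.1%)
- p0 = 2.5%: 11 of 194 (5.7%)
- p0 = 5%: 17 of 194 (8.8%)

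A result close to the floor, 4 of 194 (2.1%), has a 95% CI of 0.6% to 5.2%. That interval contains 1%, 2.5% and 5%. It lies just above 0.5% and well above 0.13%. Whether such a result stands out from normal therefore depends on the figure that the protocol leaves out.

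**Step 4: what a clear excess would mean.** Participants had coronary disease that required surgery. A prevalence above the healthy share would show that more patients lie below the limit than in a normal reference group. Without a preoperative 3D value it would not show that the difference arose after CABG.

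**The case against.** The strongest reply is that this is a prevalence study. It disclaims hypothesis testing, and reporting the share of patients below a guideline cutoff is an ordinary design. That stands: neither the estimate nor N = 194 is wrong.

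Three further points also stand.

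- The background share is an assumption. A reader might infer that cases are near certain even if CABG had no effect. The documents do not support this, since they give no basis for the 45% limit and the chance runs from 22% to over 99.9% across the shares tried.
- A reader might take 2% as the expected result or the criterion of success. Section 7.2 gives it only as a floor for detection. At an observed 10% or 20% the normal tail would be a minor explanation on the thresholds in step 3.
- 3D RV EF is not the only evidence. Section 3.3 plans a preoperative-to-follow-up comparison by 2D echocardiography. The 5.3.2 chart marks preoperative RV-GLS, FAC and TAPSE, although in brackets. The primary outcome also includes RV strain, and the chart gives a reference mean and SD for free wall strain.

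A confidence interval and a display of the distribution can be left to a statistical analysis plan, which is not at hand. The case definition, the single 3D measurement and the wording that attributes the result to CABG are fixed in this protocol, and those are the subject of this point.

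**Conclusion.** The point holds as a limit on interpretation. With the protocol as written, a 3D RV EF prevalence near the 2% floor need not differ from the normal tail, and a higher one could reflect impairment that preceded surgery. In neither case does 3D RV EF alone support an effect of CABG, as the synopsis and section 14 would have it.

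If 1% to 5% of normal subjects lie below 45%, between 1.9 and 9.7 of 194 unaffected patients would be counted as impaired, and 6 to 17 cases would be needed before the 95% CI cleared that background. With a limit as strict as 0.13% the normal tail adds about 0.25 cases and hardly matters. The caution about impairment before surgery remains whatever the share.

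A reader might go further and infer that the study is wrongly sized or cannot measure prevalence. The documents do not support that: the figure of 194 reproduces and the proportion below 45% can be estimated as planned.

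**What to change.** 1. In 7.2 and 7.4, state how the 45% limit was set and what share of normal subjects is expected below it. If the cited source gives no share, state a range and say that it is assumed.
2. Report the prevalence with its 95% CI beside that share. Describe it as exceeding the normal reference only if the lower confidence limit is above the share. Even then, do not call the excess an effect of surgery.
3. Call values under 45% below the normal limit, rather than impaired by or after CABG.
4. Reword section 14 and the synopsis objective, and 1.2 to match, so that 3D RV EF alone is not attributed to CABG. Base any statement of change after surgery on the measures with a preoperative value, that is, the 2D comparison in 3.3.

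This needs wording and one reference figure, with no new patients or measurements. The small downside is that a low prevalence can no longer be presented as RV depression caused by CABG. Statements of change will also rest on 2D measures, some of which section 2.1 itself regards as limited after cardiac surgery, so that limitation should be stated with them.

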### **7.3. Stopping rules**

Patients enrolled may withdraw voluntarily from study participation at any time and for any reason. If voluntary withdrawal occurs, the subject will be asked for permission to be followed for clinical outcome.

### **7.4. Data analyses**

Tracking of outcome measures will begin at randomization and continue until death or end of follow-up (10 years after CABG). Continuous variables will be presented as mean  $\pm$  standard deviation (SD) if normally distributed, otherwise as median with interquartile range (25th and 75th percentile), minimum and maximum values. Discrete variables will be presented in frequencies and percentages. Kaplan-Meier plots will be constructed to visualize time to event variables and log-rank tests will be used.

All statistical analyses will be done using Stata 15.0 (Stata Corp., College Station, USA). Statistical assistance is provided by the Department of Biostatistics, Aarhus University.

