## 2.2. Rationale

There remains an unresolved contradiction between the undisputable echocardiographic signs of RV depression after cardiac surgery and the lack of clinical signs of RV failure. This study seeks to contribute to a better understanding of this phenomenon.

We seek to determine the prevalence and scale of RV dysfunction two years after CABG by applying the latest available echocardiographic technology in RV evaluation. We expect the use of 3D imaging to provide better visualization of the RV's complex shape in order to allow definitive assessment of potential RV depression after CABG.

We aim to put the objective findings in relation to patient-reported outcome measures and prognosis. In addition to assessment of functional class by NYHA class, we will inquire into health-related quality of life with the disease-specific Seattle Angina Questionnaire 7 (SAQ-7) and functional capacity with the Borg CR 10® scale. Finally, we aim to examine the prognostic relevance of the phenomenon with a five- and ten-year follow-up of our patients for major adverse cardiac and cerebrovascular events (MACCE).

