### **3.3. Secondary outcomes measures**

At follow-up 24-30 months after surgery:

- Full 2D/3D Echocardiography (specified in 5.3. Endpoint Evaluations)
- Disease-specific health-related quality of life as assessed by SAQ-7
- NYHA class
- Borg CR 10®
- Graft patency as assessed by CTA
- Haemoglobin, ProBNP
- ECG

In-hospital variables:

- RV function decrement (systolic RV function preoperative versus 2-year follow-up) as assessed by 2D echocardiography
- Degree of revascularization according to the operations report (time of intervention)
- Signs of perioperative myocardial damage (CK-MB, ECG, postoperative echocardiography)

At 5- and 10-year follow-up major adverse cardiac and cerebrovascular events (MACCE) according to the electronic patient record:

- Death from any cause (cardiovascular and non-cardio-vascular mortality).
- Myocardial infarction
- Repeat hospitalization due to cardiac cause
- Cerebrovascular accident
- Repeat revascularization

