### **5.3. Endpoint Evaluations**

#### **5.3.1. Follow-up 2D/3D-echocardiography (24-30 months after surgery)**

The present Right-Heart-Substudy is designed to gain insight regarding the long-term impact of CABG surgery on right heart function. Hence, we scheduled a full 2D and 3D echocardiography with special focus on RV function at the time of SWEDEGRAFT two-year follow-up. We intend to use a GE VIVID E95 system (GE Medical System, Horten, Norway) with a 2.5-MHz transducer for transthoracic echocardiography.

For all image analysis EchoPAC version 203 (GE-Vingmed Ultrasound, Horten, Norway) will be used. All measurements will be the averaged over three consecutive heart cycles (six in terms of atrial fibrillation) in end-expiration. 3D and 2D echocardiography will be performed according to international guidelines (Lang 2015). In case of poor 3D image quality 2D images and/or a contrast agent (SonoVue/Optison) will be used to opacify both ventricles.

The following parameters will be recorded by 2-dimensional echocardiography: LVEF, left ventricular end-diastolic (LVEDV) and systolic volume (LVESV) is assessed by the biplane disc method. Left and right atrial volume will be assessed by biplane area-length method indexed by body surface area (BSA). The interventricular septum and the posterior wall thickness will be obtained from the parasternal view. LV mass is calculated and indexed according to BSA. RV systolic function is assessed by the 3D-RV EF volumetric method, RV S' is measured by lateral,

pulsed tissue Doppler velocities. In addition, TAPSE is obtained from the lateral tricuspid plane. RV strain is calculated at the RV free wall (RV-FWS), which is used as the main measure, according to the guidelines, and at the total RV wall, which includes the interventricular septum and free wall (RV-GLS) (Lang 2015).

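### Section 7.4 starts outcome tracking only at randomisation, although the RV function to be related to MACCE is first measured 24-30 months after surgery

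*Protocol*

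**What the plan says.** Section 7.4 gives one start and one end for outcomes: "Tracking of outcome measures will begin at randomization and continue until death or end of follow-up (10 years after CABG". In the same paragraph it gives the only time-to-event method: "Kaplan-Meier plots will be constructed to visualize time to event variables and log-rank tests will be used". It names no groups for the log-rank test. No section gives a second time origin, a landmark, delayed entry, or a rule that sets earlier events aside.

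Two sections describe the analysis in question. Section 2.2 says "we aim to examine the prognostic relevance of the phenomenon with a five- and ten-year follow-up of our patients", the events being MACCE and the phenomenon being RV dysfunction after CABG. Section 5.2.9 plans the 5- and 10-year record review "in order to correlate cardiac function to long-term clinical outcome".

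The follow-up RV measurement comes late. Section 5.3.1 says "we scheduled a full 2D and 3D echocardiography with special focus on RV function at the time of SWEDEGRAFT two-year follow-up", and section 4.3 puts that visit at 24-30 months after surgery. The chart in section 5.3.2 marks 3D RV EF and RV free-wall strain for the follow-up echo only. Section 3.3 also lists "RV function decrement (systolic RV function preoperative versus 2-year follow-up) as assessed by 2D echocardiography", which cannot be known before the follow-up echo either.

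Early events are recorded. Section 5.2.9 says "the MACCE rate is registered at 2-year follow-up after review of the electronic patient record", and the schedule of evaluations marks the 24-30 month MACCE item with the asterisk that denotes "Elements of the main SWEDEGRAFT study to be included in the Right-Heart-Substudy".

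**The concern.** A prognostic analysis asks whether a measurement predicts what happens after it. With randomisation as the origin, patients would be grouped by an echo done at 24-30 months, and their myocardial infarctions, strokes, repeat revascularisations and cardiac readmissions from before that echo would count as outcomes. Such an event may itself have impaired the right ventricle. The time order is then reversed, and RV dysfunction can appear prognostic when it has no effect on later events.

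Only non-fatal events can enter in this way. Section 4.1 requires the patient to be able to attend the visit, so no participant can have died before it.

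The protocol does not settle whether early events and RV function are linked. Section 1.3 treats a relation between RV dysfunction and graft patency, or perioperative myocardial damage, as a question to be studied. Section 2.1 reports evidence against an ischaemic cause. Neither a link nor its absence can be assumed.

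The reach is limited. The prevalence outcome is untouched, as are comparisons by graft arm or by preoperative or perioperative variables. MACCE is listed in section 3.3 but appears neither among the synopsis outcomes nor in the secondary objectives, and no sample size was set for it.

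**Working it through.** The protocol states no figure for this analysis, so there is none to reproduce. The sample size in section 7.2 concerns prevalence and does not bear on it.

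**Step 1: timing, from the protocol alone.** Inputs: echo at 24-30 months after surgery (section 4.3); MACCE review at 5 and 10 years after surgery (section 5.2.9). The short gap between randomisation and surgery is ignored.

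- 5-year window: 24/60 = 40% to 30/60 = 50% lies before the echo; 2.5-3 years remain.
- 10-year window: 24/120 = 20% to 30/120 = 25% lies before the echo; 7.5-8 years remain.

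**Step 2: share of first events before the echo.** The protocol gives no MACCE rate. Assume a constant first-event rate r of 3% to 10% per year. The share before time t within horizon h is (1 − e^(−rt)) / (1 − e^(−rh)).

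- 5 years, lowest: r = 0.03, t = 2: 0.418. Highest: r = 0.10, t = 2.5: 0.562.
- 10 years, lowest: r = 0.03, t = 2: 0.225. Highest: r = 0.10, t = 2.5: 0.350.
- Patients affected, of the 230 planned: 230 × (1 − e^(−0.06)) = 13.4 to 230 × (1 − e^(−0.25)) = 50.9.

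**Step 3: effect on the log-rank test (illustration only).** From the protocol: N = 230, the echo time, and the 2% prevalence in section 7.2. Assumed: 5%, 10% or 15% with a non-fatal MACCE before the echo, uniform in time; RV dysfunction in 2%, 5%, 10% or 20%; an odds ratio of 1, 1.5, 2 or 3 linking the two, with prevalence held fixed; echo time uniform on 2-2.5 years; post-echo event rate 5% per year in both groups, so the true post-echo hazard ratio is 1. The test is the first-event log-rank, (O − E)²/V against 3.841 (two-sided 5%), with 4,000 trials per scenario. The Monte Carlo standard error at 5% is √(0.05 × 0.95/4000) = 0.34 percentage points.

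Rejection rates with randomisation as origin, lowest to highest scenario:

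| Odds ratio | 5 years, all scenarios | 10 years, all scenarios | 5 years, 2% prevalence only | 10 years, 2% prevalence only |
|---|---|---|---|---|
| 1 | 4.2-6.3% | 4.4-7.3% | not shown | not shown |
| 1.5 | 6.9-13.5% | 6.0-11.2% | 7.6-10.0% | 7.7-10.4% |
| 2 | 9.4-28.3% | 7.8-19.9% | 10.5-15.5% | 9.5-13.9% |
| 3 | 14.5-59.3% | 11.6-42.8% | 14.5-26.0% | 12.0-23.0% |

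With the echo as time zero, every scenario gives 4.2-6.8% at 5 years and 4.5-6.8% at 10 years.

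**Step 4: a second set of assumptions.** First-event rate 3% or 6% per year, RV dysfunction in 10% of patients without an early event, follow-up to 10 years, 1,000 runs each. If an early event doubles the chance of RV dysfunction, the test from randomisation rejects in 13.4% (3% rate) and 19.5% (6% rate); if it triples it, 26.1% and 42.4%; if unrelated, 5.3% and 4.3%. From the echo, rejection is 3.6-5.8% throughout.

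**The case against.** The strongest reply is that section 7.4 does not make this error. It says when tracking of outcomes starts, not that randomisation is time zero for RV function against MACCE. The outcome measures in section 3.3 include in-hospital variables, so a window opening at randomisation is a natural description of data capture. No section says that RV function will be compared by log-rank, and graft arm is another possible grouping. On that reading, what remains is a detail that an analysis plan could supply.

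This stands in part, and it is why the point is conditional. But the sentence is in the data-analyses section, runs until death or end of follow-up, and sits beside Kaplan-Meier. Relating cardiac function to later events is the only purpose the protocol gives for the 5- and 10-year MACCE review. An analysis plan that took over the one stated origin would carry the problem with it.

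A second reply is that 2-year MACCE may not be in the substudy data: the list of two-year data in section 3.1 and the import list in section 8.1 both omit it. However, the schedule of evaluations marks it as included, and section 5.2.9 takes it from the patient record.

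Third, the magnitudes rest on assumptions. This stands. The 59% needs 20% prevalence, 15% early MACCE and an odds ratio of 3 together, whereas section 1.1 expects RV function to be largely maintained. At 2% prevalence only about 230 × 0.02 = 4.6 patients are affected. There, a check with 3,000 runs gave 5.7-6.4% rejection at 5 years even with no link, so part of the excess at an odds ratio of 1.5 is a small-group effect.

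**Conclusion.** The concern holds as a conditional, minor point. Randomisation is the only start the protocol gives. It does not suit the planned analysis of follow-up RV function against MACCE, because 40-50% of the 5-year window and 20-25% of the 10-year window precede the measurement. Those shares come from the protocol. The size of any bias does not: it depends on an early-event rate, a prevalence and an association that the protocol does not give, and it is zero if early MACCE and RV function are unrelated. Under the assumed ranges, an odds ratio of 2 raises false rejection from the nominal 5% to 9-28% at 5 years and 8-20% at 10 years. The conclusion also rests on reading the stated start as the analysis origin and RV function as the grouping, neither of which section 7.4 says outright.

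**What to change.** Add one or two sentences to section 7.4. For analyses relating follow-up RV function, including the decrement from the preoperative echo, to MACCE: time zero is the date of the 24-30 month echocardiogram, only later events count, and follow-up ends at 5 and 10 years after surgery. Report MACCE between surgery and the echo descriptively; it may be used as a baseline covariate. Keep randomisation or surgery as the origin for comparisons by graft arm or by preoperative or perioperative variables, noting that these still include only patients who survived to the visit.

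No new measurement is needed, since 2-year MACCE is already registered. Because sections 3.1 and 8.1 omit it from their data lists, it should be added there. The price is that pre-echo events no longer count as outcomes in this one analysis: 230 × 0.05 = 11.5 to 230 × 0.15 = 34.5, or about 12-35 patients under the assumed rates. Those patients remain at risk for later events.
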